9.5.5.2 HIF Expression

Tumor tissue samples will be analyzed for HIF-2 α and HIF-1 α expression, and for the presence of other elements of the HIF pathway.

10.0 OFF TREATMENT/OFF STUDY CRITERIA

Each subject has the right to withdraw from the study at any time without prejudice. The investigator may discontinue any subject's participation for any reason, including adverse event or failure to comply with the protocol (as judged by the investigator such as compliance below 80%, failure to maintain appointments, etc.).

Should a subject withdraw from the study, the reason must be stated on the case report form, and a final evaluation of the subject should be performed.

Patients who go off treatment must be followed for adverse events (AEs) for at least 30 days from the last dose of PT2385.

10.1 Off Treatment Criteria

1. **Disease Progression:** Remove patient from protocol therapy at the time progressive disease is documented. Disease progression is defined as: Progressive neurologic abnormalities not explained by causes unrelated to tumor progression (e.g. anticonvulsant or corticosteroid toxicity, electrolyte abnormalities, hyperglycemia, etc.) or a greater than 25% increase in the measurement of the tumor by MRI scan. If neurologic status deteriorates, on a stable or increasing dose of steroids, or if new lesions appear on serial MRI, further study treatment will be discontinued.
2. **Adverse Event:**
 - Intercurrent illness that prevents further administration of treatment
 - Patients who experience unacceptable toxicity. Patients removed from study for unacceptable adverse events will be followed until resolution or stabilization of the adverse event.
3. **Patient Withdrawal:** Patient's refusal to continue treatment: in this event, document the reason for withdrawal.

4. **Non-Compliance:** Failure to comply with protocol (as judged by the investigator such as compliance below 80%, failure to maintain appointments, etc.)
5. **Physician Decision:** If at any time the treating physician feels constraints of this protocol are detrimental to the patient's health remove the patient from protocol therapy.
6. **Protocol Defined Delay:**
 - Patients who experience a treatment-related toxicity causing a delay in treatment >21 days
 - Delay in protocol >28 days for major events or other non-treatment related delays
 - Patients who require >2 dose reductions
 - Patients who must be put on an enzyme-inducing anti-epileptic drug (EIAED) during the study
7. **Death**

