3.2 Eligibility Criteria

1. Patients must have histologically confirmed glioblastoma that is progressive or recurrent following radiation therapy and temozolomide according to the Response Assessment in Neuro-Oncology (RANO) criteria with:
 - a) New contrast-enhancing lesion outside of radiation field on decreasing, stable, or increasing doses of corticosteroids.
 - b) Increase by $\geq 25\%$ in the sum of the products of perpendicular diameters between the postradiotherapy scan with the smallest tumor measurement and a scan at least 12 weeks from completion of RT+TMZ, on stable or increasing doses of corticosteroids.

Note: clinical deterioration not attributable to concurrent medication or comorbid conditions is sufficient to declare progression on current treatment but not for entry onto a clinical trial for recurrence.

2. Tumor O(6)-methylguanine-DNA-methyltransferase (MGMT) methylation status must be available. Results of routinely used methods for MGMT methylation testing (e.g. methylation-specific polymerase chain reaction, MSPCR, or quantitative PCR) are acceptable.

3. Patients must have a tumor tissue form indicating availability of archived tissue from a previous surgery for glioblastoma, completed and signed by a pathologist. See Section [9.5.5](#).
4. Patients must have measurable (defined by at least 1 cm x 1 cm) contrast-enhancing disease by MRI imaging within 21 days of starting treatment.
5. Patients must be able to undergo MRI of the brain with gadolinium. Patients must be maintained on a stable or decreasing dose of corticosteroid regimen (no increase for 5 days) prior to this baseline MRI.
6. Patients must be in first recurrence of glioblastoma following radiation therapy and temozolomide.
7. Patients must have recovered from severe toxicity of prior therapy. The following intervals from previous treatments are required to be eligible:
 - 12 weeks from the completion of radiation.
 - 6 weeks from a nitrosourea chemotherapy
 - 3 weeks from a non-nitrosourea chemotherapy
 - 4 weeks from any investigational (not FDA-approved) agents
 - 2 weeks from administration of a non-cytotoxic, FDA-approved agent (e.g., erlotinib, hydroxychloroquine, etc.)
8. Patients must be 18 years of age or older.
9. Patients must have a Karnofsky Performance (KPS) Status \geq 60% (i.e. the patient must be able to care for himself/herself with occasional help from others).
10. Patients must have the following organ and marrow function:

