4.4 General Concomitant Medication and Supportive Care Guidelines

Prohibited Concomitant Medications During Study

Patients may receive other medications that the investigator deems to be medically necessary, with the specific exception of non-protocol specified chemotherapy, radiotherapy, anti-neoplastic biological therapy or other investigational agents. Patients who require the use of any of the aforementioned treatments for clinical management should be removed from the study.

PT2385 is primarily metabolized by UGT2B17, UGT2B7, UGT2B15, CYP2C19 and CYP3A4. Strong inhibitors of CYP2C19 and CYP3A4 should be avoided in patients receiving PT2385 ([Appendix II](#)).

PT2385 has been shown to induce the enzymes CYP3A4 and CYP2B6 in cultured human hepatocytes. Simcyp PBPK model simulations indicate weak-to-moderate CYP3A4 substrate midazolam DDIs (~50% reduction in midazolam AUC) at the clinically relevant PT2385 doses. Simulations also indicate that PT2385 is a weak CYP2B6 inducer (< 11% AUC reduction for CYP2B6 substrate bupropion at the clinically relevant PT2385 doses). PT2385 is not a potent inhibitor for CYP1A2, CYP2B6, CYP2C8, CYP2C9, CYP2C19, CYP2D6 and CYP3A4 ($IC_{50} > 8.8 \mu\text{g/mL}$). It is unlikely to significantly inhibit these CYPs at the clinically relevant PT2385 concentrations ($C_{\text{max}} \sim 3.14 \mu\text{g/mL}$). A partial list of CYP3A4, CYP2B6, CYP2C9, and CYP2C19 substrates is provided in [Appendix III](#).

Patients taking medications metabolized by CYP3A4 and CYP2B6 should be monitored carefully for decreases in drug effect. Patients taking medications metabolized by CYP2C9 and CYP2C19 should be monitored for potential increases in drug effect.

Corticosteroids

Postoperatively, corticosteroids should be tapered to a stable dose as determined by the clinical status of the patient. The lowest required steroid dose should be maintained throughout the duration of the study in order to eliminate steroid effects as a confounding variable in the interpretation of serial brain imaging studies. Corticosteroid doses can be tapered as clinically indicated if the patient appears to be responding to therapy as judged by serial scans. Corticosteroid dose may, of course, be increased in the event of clinical deterioration or at the discretion of the attending physician. In the event of suspected clinical deterioration, repeat brain imaging is recommended.

Anticonvulsants

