- e) The corticosteroid dose at the time of the scan evaluation should be no greater than the dose at time of baseline scan.
- f) Stable or improved non-enhancing (T2/FLAIR) lesions on same or lower dose of corticosteroids compared to baseline scan. g) Stable or improved clinically.

Note: Subjects with non-measurable disease cannot have a partial response. The best response possible is stable disease.

Stable Disease – SD (requires *all* of the following):

- a) Does not qualify for CR, PR, or progressive disease (PD).
- b) The designation of stable disease requires a minimum of 4-week duration.
- c) All measurable and non-measurable sites must be assessed using the same techniques as baseline.
- d) Stable non-enhancing (T2/FLAIR) lesions on same or lower dose of corticosteroids compared to baseline scan. In the event that the corticosteroid dose was increased for new symptoms and signs without confirmation of disease progression on neuroimaging, and subsequent follow-up imaging shows that this increase in corticosteroids was required because of disease progression, the last scan considered to show stable disease will be the scan obtained when the corticosteroid dose was equivalent to the baseline dose. e) Stable clinically.

Progressive Disease – PD (defined by *any* of the following):

- a) $\geq 25\%$ increase in sum of the products of perpendicular diameters of enhancing lesions compared to the smallest tumor measurement obtained either at baseline (if no decrease) or best response, on stable or increasing doses of corticosteroids.*
- b) Significant increase in T2/FLAIR non-enhancing lesion on stable or increasing doses of corticosteroids compared to baseline scan or best response following initiation of therapy,* not due to co-morbid events (radiation therapy, demyelination, ischemic injury, infection, seizures, postoperative changes, or other treatment effects). c) Any new lesion.
- d) Clear clinical deterioration not attributable to other causes apart from the tumor (e.g., seizures, medication adverse effects, complications of therapy,

cerebrovascular events, infection, etc.) or changes in corticosteroid dose. The definition of clinical deterioration is left to the discretion of the treating physician, but it is recommended that a decrease in 20% of KPS or from any baseline to 50% or less be considered, unless attributable to comorbid events.

- e) Failure to return for evaluation due to death or deteriorating condition.

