- f) Clear progression of non-measurable disease.

* Stable doses of corticosteroids include patients not on corticosteroids.

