9.0 MONITORING OF PATIENTS

9.1 Table of Required Observations

PT2385 (28-Day Cycles)

	Baseline	Days 1-28 of every cycle	Cycle 1	Weekly During Cycle 1	Weekly During All Cycles	Pre-Odd Cycles (cycles 3+)	Pre-Even Cycles	Off Treatment	30 Days post-last dose
PT2385		6							
Glucocorticoids Dose Evaluation	1					5		8	
AE Evaluation	1			7		5	5	8,10	11
MRI	1,15					5		8	
H&P/Neuro Exam	1					5	5	8	
KPS	1					5	5	8	
Vital Signs with pulse oximetry	1,2			2,7		2,5	2,5	2,8	
CBC, Diff, Platelets	1				9,7	5,9	5,9	8	
Serum Chemistry	1,3			3,7		3,5	3,5	3,8	
APTT or PTT	1								
Serum Pregnancy Test	1,4								

Plasma Samples for Pharmacokinetics			12						
Plasma Samples for Pharmacodynamics			13						
Plasma Sample for Pharmacogenomics	14								
Archived Tumor Tissue	16								

- 1– All baseline measurements must be done within minus 21 calendar days of treatment administration unless otherwise specified.
- 2– Including blood pressure, respiratory rate, heart rate, temperature, weight, height: height is required at baseline only; weight is required at pre-odd cycle evaluations only. Patients with dyspnea or asymptomatic desaturation (oxygen saturation <92%), will be further evaluated as clinically indicated: evaluation may include chest x-ray, arterial blood gas analysis, pulmonary function testing including diffusion capacity, co-oximetry, as well as evaluation for specific causes of hypoxia/dyspnea.
- 3– Including albumin, alkaline phosphatase, total bilirubin, calcium, creatinine, magnesium, phosphorus, potassium, SGOT, SGPT, sodium.
- 4– For women of child-bearing potential.
- 5– Within minus 5 calendar days of cycle start.
- 6– PT2385 is administered orally twice daily on Days 1-28 of each 28-day cycle (see Section [4.3.1](#)). Patients are required to keep a medication diary. 7– ± 1 day
- 8– Evaluations done within +7 days of off treatment date unless indicated: do not repeat: if MRI within minus 14 days of off-treatment date; if H&P/neuro, KPS, labs within minus 5 days of off-treatment date.
- 9– If ANC < 1500 or plts < 100,000, CBCs/differentials will be repeated twice a week until counts are recovered (ANC ≥1500 or plts ≥100,000) per protocol. If counts are recovered (ANC ≥1500 or plts ≥100,000) on day of scheduled drawing do not repeat until next protocol schedule day
- 10 – Adverse Events must be followed for at least 30 days from last dose of PT2385.
- 11– Perform within +14 days of the 30-day post-last dose date.

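### Section 10.1 stops drug for tumor growth during a steroid taper that Section 8.1 does not count as progression, and Section 11 does not restate which rule defines the PFS event

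*Combined protocol and SAP*

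**What the plan says.** **Stopping rule.** Section 10.1 item 1 removes the patient once progression is documented and then defines progression itself, without citing Section 8.1 or RANO. One limb is "a greater than 25% increase in the measurement of the tumor by MRI scan". Steroids qualify only a different limb: "If neurologic status deteriorates, on a stable or increasing dose of steroids".

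**RANO rule.** In Section 8.1, progression criterion (a) is an increase of at least 25% in the sum of products, "compared to the smallest tumor measurement obtained either at baseline (if no decrease) or best response, on stable or increasing doses of corticosteroids". A footnote counts patients not on steroids as stable, so only falling doses are left out. Criterion (b) is "Significant increase in T2/FLAIR non-enhancing lesion on stable or increasing doses of corticosteroids" and criterion (f) is "Clear progression of non-measurable disease". Section 10.1 item 1 lists neither.

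**Entry rule.** Section 3.2 item 1b requires growth shown on "a scan at least 12 weeks from completion of RT+TMZ, on stable or increasing doses of corticosteroids".

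**Taper.** Section 4.4 says: "Corticosteroid doses can be tapered as clinically indicated if the patient appears to be responding to therapy as judged by serial scans".

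**PFS.** Section 11 runs PFS from treatment start to the date progression is judged to have occurred and names no criterion. It censors patients without progression at their last tumor assessment and has a separate rule for deaths without reported progression. Section 9.5.4, on exploratory imaging, says that efficacy, including PFS, rests on RANO alone.

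**After stopping.** Footnote 8 to the Section 9.1 table covers the off-treatment MRI: "do not repeat: if MRI within minus 14 days of off-treatment date". Section 10.2 then schedules survival follow-up only. Section 4.1 says all patients are followed for PFS but gives no MRI schedule after treatment.

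**The concern.** Two rules for the same event differ on a condition that matters in glioblastoma imaging. RANO does not count enhancement that grows while steroids are being reduced, and the entry criteria apply the same condition. Section 10.1 is the outlier.

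The patient caught between the rules is one the protocol itself creates: apparently responding, tapered for that reason, then showing more than 25% growth. Section 4.1 continues drug until the progression or other off-treatment criteria are met and points to Section 10.0, so sites will look to 10.1 when deciding to stop.

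Two things are at stake. A patient without RANO progression can lose the drug, and that patient's PFS can be recorded as an event or as a censoring depending on which section the site follows.

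**Working it through.** **1. The rules side by side**, for growth above 25% during a taper, with no new lesion, no clinical decline and no other trigger.

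- Section 8.1: criterion (a) fails because the dose is decreasing. Not progression.
- Section 10.1 item 1: the size limb is met. Progression, drug stopped.
- PFS under Section 9.5.4 with Section 11: no RANO progression, so censored at the last assessment, or dated at death if the death rule applies.
- PFS under Section 11 with the 10.1 definition: progression was declared, so an event at the stop.

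The converse gap is secondary. Progression by criterion (b) or (f) does not by itself meet the 10.1 definition. This bears on time on drug, not on the PFS date. The difference between more than 25% and at least 25% is trivial.

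**2. The plan's own figures.** The plan gives no figure on this point. Its response design reproduces exactly (24 then 35 patients, stop at 1 or fewer responses, reject at 5 or more). Early stopping has probability 0.661 at a 5% response rate and 0.033 at 20%. Power is 0.852 and attained alpha 0.028. None of these uses PFS or the 10.1 definition.

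**3. Size of one misclassified patient (illustration).** Section 11 names no landmark. Six months (26 weeks) is used because Section 2.1 quotes 6-month PFS of 10–15% for salvage chemotherapy.

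Inputs:
- MRI every 8 weeks (Section 4.1).
- Assumed: the affected patient stops at week 16, since a taper for apparent response follows the week-8 scan.
- Assumed, N=35: the other 34 progress 17, 9 and 4 at weeks 8, 16 and 24, with 4 free. An exponential curve with 10% free at 26 weeks leaves 16.7, 8.2 and 4.1 of 34 free at those scans, against 17, 8 and 4 here.
- Assumed, N=24: the other 23 progress 12, 5 and 3, with 3 free.

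Kaplan-Meier product at 26 weeks:

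| Affected patient | N=35 | N=24 |
|---|---|---|
| Event at week 16 | 18/35 × 8/18 × 4/8 = 4/35 = 11.4% | 12/24 × 6/12 × 3/6 = 3/24 = 12.5% |
| Censored at week 16 | 18/35 × 9/18 × 4/8 = 9/70 = 12.9% | 12/24 × 7/12 × 3/6 = 7/48 = 14.6% |
| Dated at a death after 26 weeks | 5/35 = 14.3% | 4/24 = 16.7% |

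Event versus censored differs by 1.4 points (N=35) and 2.1 points (N=24). Event versus late death differs by 1/35 = 2.9 and 1/24 = 4.2 points.

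Now let three others be censored just after week 8, one each from the week-16, week-24 and free groups:

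- N=35: event 18/35 × 6/15 × 3/6 = 10.3%; censored 18/35 × 7/15 × 3/6 = 12.0%; late death 18/35 × 4/15 = 13.7%.
- N=24: event 12/24 × 4/9 × 2/4 = 11.1%; censored 12/24 × 5/9 × 2/4 = 13.9%; late death 12/24 × 3/9 = 16.7%.

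The differences from an event become 1.7 and 2.8 points (censored) and 3.4 and 5.6 points (late death).

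**4. Against sampling error.** Exact 95% intervals are 3.2% to 26.7% for 4/35 and 2.7% to 32.4% for 3/24.

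**5. A second assumed pattern.** With 35 patients progressing 18, 8, 4, 3 and 2 at weeks 8 to 40, censoring one of the week-16 events moves 26-week PFS from 14.3% to 15.9%, and censoring four moves it to 20.6%. The median stays at 8 weeks.

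**The case against.** The strongest reply is that PFS is already settled. Section 9.5.4 ties PFS to RANO alone, Section 8.1 defines RANO progression, and Section 11 says what to do with patients who have not progressed. Steroid dose is evaluated at the visits with an MRI, so the statistician can apply Section 8.1 to the removal scan whatever 10.1 says. Most of this stands. A reader might infer that the plan leaves PFS dating wholly open; the documents do not support that, and the reading they favour is censoring or death. What remains is a residual ambiguity: the RANO sentence sits in an exploratory imaging section, Section 11 names no criterion, and 10.1 labels its own rule disease progression.

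A second reply is that a stopping rule may be broader than an endpoint definition, and that Sections 10.0 and 10.1 item 5 already let the investigator or treating physician stop. That is fair as a principle and softens the T2/FLAIR and non-measurable omissions. But 10.1 does not present a deliberately wider stopping rule; it defines progression, differently from Section 8.1.

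A third reply is that the case is narrow and its effect small. That stands and sets the grade.

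A reader might also blame 10.1 for the missing later scan. The lack of a post-treatment MRI schedule applies to every reason for stopping. It only means that RANO progression after such a stop would usually go unobserved.

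**Conclusion.** The conflict between Sections 10.1 and 8.1 holds as written; severity is minor. Following 10.1 can remove a patient who has not progressed by RANO. How that stop enters PFS is favoured one way by the text but not stated where the analysis is defined.

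The effect is on time on drug and on PFS, a descriptive secondary endpoint with no decision rule. Frequency cannot be derived from the documents. Per affected patient, 6-month PFS shifts by about 1.4 to 2.8 points for event versus censored, and 2.9 to 5.6 points for event versus a death after 6 months. These figures rest on the assumed progression patterns, the week-16 stop and the added censorings, and are small against the sampling error.

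A reader might infer that the primary endpoint is compromised. The documents do not support that: the two-stage rule and its error rates do not use PFS or the 10.1 definition. At most, response could be touched indirectly, because it is counted during treatment.

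**What to change.** In Section 10.1 item 1, replace the free-standing definition with progressive disease per RANO as defined in Section 8.1. In Section 11, state that the PFS event is Section 8.1 progression or death. The first change also brings T2/FLAIR and non-measurable progression into the stopping rule. As an option, record on the case report form which 8.1 criterion led to removal, and list removals for progression that did not meet 8.1.

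The cost is one cross-reference and one sentence. No patients or new procedures are added, and the Section 9.1 table already has steroid dose evaluated at baseline, before odd-numbered cycles and at the off-treatment visit. The one downside is that an affected patient stays on drug and on the regular 8-week MRI schedule until Section 8.1 is met. The investigator can still stop earlier under Section 10.0 or 10.1 item 5.

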10.2 Off Study Criteria

Patients will only be off study at the time of death. All patients will be followed for survival every 2 months for the first two years from the off treatment date; after 2 years, patients will be followed every 6 months until death. Survival status may be obtained by phone call, clinic visit, or medical records (e.g. physician notes/laboratory results of clinic or hospital visit). Please note that additional survival status reports will be required twice yearly for ABTC Central Office reporting.

11.0 STATISTICAL CONSIDERATIONS

Primary Objectives

To estimate tumor objective response rate. The tumor response includes complete response (CR) and partial response (PR) per RANO criteria.

Secondary Objectives

1. To determine the safety of oral PT2385 800 mg twice daily in patients with recurrent glioblastoma
2. To estimate overall survival
3. To estimate progression-free survival

Exploratory Objectives

1. To describe the pharmacokinetic and pharmacodynamic properties of PT2385 in patients received PT2385 800 mg twice daily, continuously in 28-day per cycle.
2. To describe baseline intratumoral hypoxia using MR-based neuroimaging sequences.

Sample size justification

This is a single-arm, open label, multi-institutional, non-randomized safety and efficacy study in patients with first recurrence of GBM. The primary endpoint is tumor radiographic response (PR+CR). The study hypothesizes the single agent of PT2385 will achieve at least 20% radiographic response rate. The 20% response rate is considered clinically meaningful compared to a null hypothesis of 5% response rate (Taal et al., 2014).

The sample size estimation is based on a 2-stage design (minimax) with 85% statistical power and a false positive rate at 5%. At the first stage, 24 patients will be enrolled onto the study. The trial will be stopped and accept the null hypothesis if the response rate is less than or equal to 1/24. Otherwise, the study will continue to stage 2. The probability of early stopping for futility is 0.661 when the null is true and 0.033 when a true response is 20%. Eleven additional patients will be enrolled on the second stage of the trial. If 5 out of 35 patients have an objective response, the study will reject the null hypothesis to conclude PT2385 is effective to treat patients with first recurrence of glioblastoma.

Analysis Plan

General considerations:

The primary efficacy analysis will be performed on the Intent-to-Treat (ITT) population which is defined as all subjects who were enrolled onto the study. The primary safety analysis will be performed on the safety population who received at least one dose of study drug.

Objective response rate

To estimate tumor objective response rate, the proportion of patients who had objective partial response (PR) or complete response (CR) during the course of the treatment will be estimated along with 95% confidence intervals using the exact binomial method.

Overall Survival

To estimate overall survival, survival time is defined as the time from the date of treatment start to the date of death occurrence /or censored at the time of last known

alive. Survival probability and median time survival will be estimated using KaplanMeier method along with 95% confidence interval.

Progression-free Survival

To estimate progression-free survival (PFS), progression-free survival time is defined as the date of treatment start to the date progression was deemed. Probability of PFS and median of PFS will be estimated using Kaplan-Meier method along with 95% confidence interval.

Date of progression will not be imputed for patients with missing tumor assessment(s) during planned tumor assessment. Patients who died without a reported progression, with complete scheduled imaging scans will be considered to have progressive disease on the date of death. Patients who did not have disease progression or died with more than two missing planned MRI scans will be censored at the date of last tumor assessment.

Safety/Toxicity

NCI Common Terminology Criteria for Adverse Events (CTCAE) version 4.0 will be used for scoring toxicity and adverse events until March 31, 2018; CTCAE version 5.0 will be utilized beginning April 1, 2018. The severity and frequency of toxicity will be tabulated using descriptive statistics. The proportions of subjects who experienced grade 3 or above toxicities will be estimated, along with 95% confidence intervals by each type of toxicity.

Pharmacokinetics

Pharmacokinetic analyses are generally in descriptive nature and they will be performed with Phoenix® WinNonlin® software. PK parameters, including area under the curve (AUC), and maximum concentration (Cmax) at 6 hours post-dose, will be determined for PT2385 and PT2639 (i.e. primary inactive metabolite). Each PK parameter will be summarized descriptively (n, arithmetic mean, standard deviation, minimum, median, maximum, and coefficient of variation). Geometric means will be reported for AUC and Cmax parameters. For PK analysis, PT2385 and PT2639 plasma concentrations that are below the limit of quantitation of the assay will be censored during analysis. Standard clinical trial monitoring and data management practices will be used to ensure the integrity of study data.

Pharmacodynamics

The plasma concentration level of each exploratory Pharmacodynamic marker (i.e. EPO, VEGF) will be summarized descriptively (arithmetic mean, standard deviation) at each sample collection time point (pretreatment, 6-hours post-dose, steady state, progression). Their changes from baseline will be presented using standard descriptive statistics and

graphic summaries. Possible association between changes of concentration and clinical outcomes could be explored using statistical modeling techniques.

Hypoxia Imaging

Hypoxia imaging is strictly exploratory. The objective is to describe tumoral hypoxia using advanced MR-based sequences prior to treatment initiation in patients with recurrent GBM. Advanced MRI imaging including CEST and rOEF will be postprocessed as per standard protocols including motion and inhomogeneity correction prior to analysis. Post-processing will be performed by [name] (UCLA, ABTC Imaging Core).

Measurements of Acidic Tumor Volume: Relative pH assessed using MTR_{asym} at 3ppm will be calculated by first performing B_0 homogeneity correction, then calculating the difference in signal intensity between positive and negative offset frequencies divided by the signal intensity with no saturation, $(S_{+3ppm} - S_{-3ppm})/S_0$, for each image voxel. Acidic tumor will be defined as having $MTR_{asym} @ 3ppm > 5\%$ as determined empirically (Harris et al., 2015). Both mean $MTR_{asym} @ 3ppm$ and volume of acidic tumor within contrast enhancing and/or T2 hyperintense tumor regions will be used as exploratory measures of tumor acidity.

Measurements of Hypoxic Tumor Volume: The blood oxygenation-based reversible transverse relaxation rate, R_2' , has been shown to be directly proportional to relative oxygen extraction fraction (rOEF), scaled by the relative cerebral blood volume (rCBV) (Hirsch et al., 2014; Toth et al., 2013). In the current study we will estimate R_2' using T_2 and T_2^* measurements obtained from the ME-SAGE component of the acquisition [$R_2' = (1/T_2^*) - (1/T_2)$]. If available, we will use rCBV measurements from dynamic susceptibility contrast (DSC) perfusion MRI to estimate $rOEF$ ($rOEF = R_2'/(c * rCBV)$, where c is a constant relating to the specific static magnetic field strength). Both mean R_2' and estimates of $rOEF$ within contrast enhancing and/or T2 hyperintense tumor regions will be used as exploratory measures of tumor hypoxia.

Baseline tumor acidity and hypoxia will be defined both as continuous (e.g. mean $MTR_{asym} @ 3ppm$, mean R_2' , etc.) as well as categorical variables (i.e. acidic/hypoxic vs non-acidic/hypoxic) based on $>50\%$ of tumor having an acidic signature ($>3\% MTR_{asym} @ 3ppm$) or hypoxic signature ($R_2' > 5 s^{-1}$).

Descriptive statistics including the proportion of acidic/hypoxic and non-acidic/hypoxic lesions will be estimated with 95% confidence intervals. Fisher's exact test or other nonparametric analysis methods will be used to explore potential correlations between tumor acidity/hypoxia (imaging categorical variable) and tumor radiographic response.

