1.0 OBJECTIVES

Primary Objective

To estimate the efficacy of PT2385 as measured by radiographic response rate (by Response Assessment in Neuro-Oncology, RANO, criteria) in patients with recurrent glioblastoma

Secondary Objectives

1. To estimate the efficacy of PT2385 as measured by progression free and overall survival in patients with recurrent glioblastoma
2. To determine the safety of oral PT2385 in patients with recurrent glioblastoma

Exploratory Objectives

1. To describe the pharmacokinetic and pharmacodynamic properties of PT2385 in patients with recurrent glioblastoma
2. To describe baseline intratumoral hypoxia using novel, advanced MR-based neuroimaging sequences in patients with recurrent glioblastoma
3. To explore genetic polymorphisms involved in the metabolism of PT2385

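### The planned exact binomial interval for the response rate takes no account of the two-stage stopping rule, so its limits are out of order at low counts; a two-stage exact interval is a cheap, minor improvement

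*Combined protocol and SAP*

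**What the plan says.** Section 1.0 states the primary objective as estimation: "To estimate the efficacy of PT2385 as measured by radiographic response rate". Section 11.0 (Sample size justification) sets a minimax two-stage design with 85% power and a 5% false positive rate, testing a "null hypothesis of 5% response rate" against a 20% target: "The study hypothesizes the single agent of PT2385 will achieve at least 20% radiographic response rate". The stopping and decision rules are:

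- After 24 patients: "The trial will be stopped and accept the null hypothesis if the response rate is less than or equal to 1/24".
- Otherwise: "Eleven additional patients will be enrolled on the second stage of the trial".
- At the end: "If 5 out of 35 patients have an objective response, the study will reject the null hypothesis".

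Under Objective response rate, the same section says that the proportion of responders "will be estimated along with 95% confidence intervals using the exact binomial method". Section 11.0 does not say that the interval allows for the interim stop, and it does not say whether the 5% false positive rate is one-sided or two-sided.

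**The concern.** An exact interval takes its limits from the true sampling distribution of the result. The ordinary binomial interval treats 35 as a fixed sample size. In this trial 35 is reached only after at least 2 responses in 24, so 0/35 and 1/35 cannot occur; those trials end at 0/24 or 1/24. The ordinary interval at 35 therefore uses the wrong tail probabilities, and the error is largest at the counts nearest the futility boundary.

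Because estimation is the primary objective, this interval is a main reported result, and 20% is the value a reader will look for in it. At 2/35 the report would appear to rule out 20%. A trial that stopped for futility at 1/24 would not. The better result would look like stronger evidence against the drug.

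**Working it through.** **Inputs (all Section 11.0).** Null rate 5%; target 20%; first stage 24, stop at 1 or fewer; 11 more patients, total 35; reject at 5/35, taken as 5 or more. The interval is taken to be Clopper-Pearson.

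**1. Reproduce the plan's design figures.** Let X1 ~ Binomial(24, p) and X2 ~ Binomial(11, p).

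- Early stopping = P(X1 ≤ 1). At 5%: 0.95^24 + 24 × 0.05 × 0.95^23 = 0.292 + 0.369 = 0.661. At 20%: 0.0047 + 0.0283 = 0.033. Both match the plan.
- P(X1 ≥ 2 and X1 + X2 ≥ 5) = 0.0284 at 5% and 0.852 at 20%. Both meet the stated 5% and 85%.

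The design is sound. Only the interval is in question.

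**2. Tail probability at 2/35 for a true rate of 20%.** The possible results, from worst upward, are 0/24, 1/24, 2/35, 3/35 and so on. Ending at 2/35 needs exactly 2 responses in stage 1 and none in stage 2: C(24,2) × 0.2² × 0.8^22 × 0.8^11 = 0.0815 × 0.0859 = 0.0070.

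- Under the design: P(2/35 or worse) = 0.0047 + 0.0283 + 0.0070 = 0.040.
- Fixed sample of 35: P(X ≤ 2) = 0.019.

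The first exceeds 0.025, so inverting the design's own distribution keeps 20% inside the interval. The second is below 0.025, so the ordinary interval drops it.

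**3. Limits.** The ordinary limits are Clopper-Pearson. Each two-stage limit is the value of p at which the design-based tail probability equals 0.025, using the ordering above.

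| Result | Ordinary 95% | Two-stage 95% |
|---|---|---|
| 0/24 | 0 to 14.2% | 0 to 14.2% |
| 1/24 | 0.1% to 21.1% | 0.1% to 21.1% |
| 2/35 | 0.7% to 19.2% | 1.0% to 21.8% |
| 3/35 | 1.8% to 23.1% | 2.0% to 23.9% |
| 4/35 | 3.2% to 26.7% | 3.3% to 27.0% |
| 5/35 | 4.81% to 30.26% | 4.83% to 30.31% |

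The ordinary upper limits fall from 21.1% to 19.2% between 1/24 and 2/35. The two-stage limits rise throughout. From 4/35 upward the methods differ by at most about 0.24 percentage points.

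**4. Coverage under the design, by exact enumeration over true rates.**

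- Ordinary: minimum 94.8%, at a true rate of about 21.5%. It is below 95% only for true rates of about 21.1% to 21.5% and 23.1% to 23.9%. The upper-side miss peaks at 3.19%, just above 23.06%, where 0/24, 1/24, 2/35 and 3/35 all have upper limits below the truth.
- Two-stage: minimum 95.2%, with at most 2.5% missed on each side.
- Ordinary at a true rate of exactly 20%: only 0/24 (0.47%) and 2/35 (0.70%) have upper limits below 20%, so the upper miss is 1.17%. The lower miss is 1.42%, and coverage is 97.4%.

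**5. How often it would matter.** The probability of ending at 2/35 is 12.7%, 8.5% and 0.7% at true rates of 5%, 10% and 20%. For 2/35 or 3/35 together it is 25%, 26% and 4%.

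**The case against.** The strongest reply has four parts.

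- **No decision uses the interval.** The plan decides by count, and 2/35 fails the 5/35 rule with either interval. This stands.
- **The coverage loss is trivial.** It is at most about 0.2 points, in two narrow ranges of true rate. This stands, and it keeps the point minor.
- **The method is inferred.** The plan says exact binomial; it neither says fixed-sample nor excludes a design-based calculation. This is fair. But if a two-stage interval was intended, the text does not say so, and the same added sentence is needed.
- **The replacement assumes exactly 24 and 35.** The ITT set is everyone enrolled, so the numbers analysed could differ from plan. This stands, and the wording below allows for it.

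A reader might go further and infer that the planned interval wrongly rules out the target, or under-covers at 20%. The documents do not support that. At a true rate of 20% the ordinary interval covers 97.4% of the time and misses on the upper side only 1.2% of the time. What fails at 2/35 is coherence: the limits are out of order, and the tail probability behind the limit is 1.9% where the design gives 4.0%.

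A reader might also see a contradiction at exactly 5/35, where the rule rejects 5% but the 95% interval includes it. That is a separate matter. The lower limit is 4.81% or 4.83% depending on method, so a two-stage interval does not remove it. It arises because the rule's 5% is in effect one-sided (an inference, since the plan does not label it) while the interval is two-sided.

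**Conclusion.** The point holds as a minor one. Read as Clopper-Pearson, the planned interval is not exact under the 24/35 design and orders 1/24 and 2/35 inconsistently. The material effect is at 2/35, where the upper limit is 19.2% against 21.8%, and less at 3/35 (23.1% against 23.9%). It is a coherence and low-count defect. It does not invalidate the primary analysis, the decision rule or the sample size.

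The conclusion assumes that the unlabelled method is the ordinary interval, that the stopping rule is followed, that the analysis is at exactly 24 or 35 patients, and that 5 out of 35 means at least 5.

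**What to change.** State in Section 11.0, under Objective response rate, that the 95% interval is a two-stage exact interval using stage-wise ordering, computed with the actual stage sizes if enrolment differs from 24 and 35. It should be named before results are known, because choosing the method after seeing 2/35 would look selective.

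The cost is one or two sentences and a short routine that standard binomial software does not supply directly. The upper limits become slightly wider at low counts. Conduct, sample size and the decision rule are untouched.

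Optional and separate: state that the 5% false positive rate is one-sided, and report a one-sided 95% two-stage lower bound beside the decision. That bound is 5.8% at 5/35 and 4.1% at 4/35, and it agrees with the count rule at every possible outcome. The cost is one more figure to explain.
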